5.3 Preparation and Administration of Study Device

The bone graft particles will be prepared and mixed according to the surgical protocols set for the study. Sterile material is rehydrated with sterile saline mix, and packed into sterile bone syringes. These are used to condense the material into the sinus augmentation site at the appropriate stage of surgery.

5.4 Subject Compliance Monitoring

Subjects will be followed at routine clinical follow up visits as shown in the study steps, and monitored for adverse events. The most sensitive time is the first month after implantation which is a risk of infection. Once the first month is crossed we don't anticipate any risk but we will keep monitoring with post-operative visits and instructions on oral hygiene.

5.5 Prior and Concomitant Therapy

Subjects will have no restrictions on their current medications. There are no study medications as such, however, peri-operative antibiotics, and analgesics will be prescribed per standard of care. Prescription antimicrobial mouth rinse will be prescribed (chlorhexidine gluconate), per standard of care.

5.6 Study Materials/ Components

5.7.1: Study Material

1. Single use grafting material only.
2. The box is non-sterile and is used to protect the graft material during shipping and storage.
3. Additional product will be available in case of unexpected need during the procedure.
4. The box contains double-barrier packaged product, the package insert, patient implant stickers and Tissue Utilization Record from the box.

CONFIDENTIAL

This material is the property of the NYU College of Dentistry. Do not disclose or use except as authorized in writing by the study sponsor

5. Prior to use the product will be inspected, including all packaging and labeling materials carefully including: no past expiration date specified on the product label, damaging to packaging, and/or a discrepancy in label information will be returned with flaws in the sterile barrier to RTI Biologics, Inc.
6. To prevent contamination of the implant, sterile technique for preparation and implantation will be used.

5.7.2: Storage Conditions.

The study material will be stored in a clean, dry environment at the temperature range specified on the product label and kept away from sunlight.

5.7 Randomization

This is a single (subject) masked study. Subjects will be unaware of which side of their jaw received which type of bone grafts. Laboratory technicians will be masked when analyzing the bone core samples.

Each tooth sites will be randomized 1:1 into one of the following bone grafts:

- Bone graft A: A mixture of 25% small-particle cortical allograft, 25% large-particle cortical allograft, 25% small-particle cancellous allograft, and 25% large-particle cancellous allograft is used for one sinus (N=10).
- Bone graft B: 100% large particle cancellous allograft for the contralateral sinus (N=10).

A randomization schedule established by an independent statistician affiliated with the New York University College of Dentistry.

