3.1 General Design

The proposed study is a Randomized, single-masked, split-mouth, single center study.

About 20 subjects will be screened in order to randomize 10 study subjects. 10 patients who needing bilateral sinus augmentation procedure using the lateral window technique will be randomized using computer generated randomized technique.

Pre-surgical Plan:

All procedures below are standard of care. Cone beam computed tomography (CBCT) scans are obtained for each patient (NYUCD radiology department). Standardization was done for the radiographic evaluations and measurements are for each patient is made using a radiographic guide. In cases of abnormal thickening of the membrane, suspected cysts or tumors in the sinus, patients are referred to an otolaryngologist (ENT). All patients are prescribed antibiotic and Flonase to be initiated one hour prior to the surgery (Augmentin 875 mg two times a day for 10 days; or ciprofloxacin 500 mg two times a day for 10 days in case of penicillin allergy) in order to minimize risk of infection and to control postoperative discomfort.

Surgical Procedure:

The sinus augmentation procedure is standard of care.

The use of different size and type (cortical or cancellous) of bone graft material for the two sites in order to evaluate the difference in outcome (if any), is for research purposes.

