3.3 Secondary Study Endpoints

We will be checking for bone volume stability through CBCT analysis comparing it from the time of placement, 8 months post-grafting and one-year post implant insertion.

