4.3 Subject Recruitment

Potential subjects are regular patients at NYUCD Department of Periodontics and Implant Dentistry and completing planned treatment. Subjects will be offered the opportunity to participate in a randomized, split mouth study comparing bone graft particle size. Written and verbal consent will be obtained. Patients/subjects will be free to 'opt out' of the study without consequence to their clinical care.

Both sizes of graft material that will be used for the study are also utilized by the clinicians for sinus augmentation procedures. To date there are no specific guidelines as to which particle size is more favorable and therefore should be exclusively used for the sinus augmentation procedures.

Bone core will be collected for research purposes during your implant surgery. These bone specimens are otherwise discarded. Personal identifying information will not be used in the analysis. Bone specimens will be coded and not identifiable by laboratory personnel or clinical investigators in this study. Only authorized study personnel will have access to the specimen-coding scheme, which will be kept in a locked file cabinet accessible only to the study investigators. No patient likenesses or personal identifying information will be used in publications or presentations.

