5.8.4 Return or Destruction of Study-Device

At the completion of the study, there will be a final reconciliation of device shipped, device consumed, and device remaining. This reconciliation will be logged on the device log form, signed and dated. Any discrepancies noted will be investigated, resolved, and documented prior to return or destruction of unused study device. Device destroyed on site will be documented in the study files.

Since the study bone graft material is used routinely in the clinic, residual material is discarded. As such there will be no residual study material to reconcile.

CONFIDENTIAL

This material is the property of the NYU College of Dentistry. Do not disclose or use except as authorized in writing by the study sponsor

6 Study Procedures

See an example of such a schedule of events at the end of this document. All procedures are standard of care unless indicated otherwise. All procedures will be performed by the study investigators who are licensed and privileged to do so.

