7.2 Statistical Methods

The primary outcomes for this study are percent vital bone, and residual graft material. Patient age, sex, and health status will be described. Two test site bone biopsies will be compared with regard to microscopic measures of percent vital bone and residual graft material. The average of three histological specimens for each test sites of the subject biopsy will be calculated. Mean percent vital bone and percent residual graft material and standard deviations for each condition will be calculated. Previous studies indicate that the primary outcome variable is normally distributed. Tests for normalcy will be done. In the event that the distributions are skewed, and appropriate non-parametric test will be used. Otherwise, comparisons of the two conditions will be made by two sided paired t-test. A p value less than 0.05 will be considered significant. Radiographic examinations will be quantified by measuring bone height at three sites at each sinus augmentation site and then averaged for analysis.

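### The plan neither codes the CBCT scans nor masks whoever measures them, and section 8.4 conflicts with section 5.7 on whether the principal investigator is masked

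*Combined protocol and SAP*

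**What the plan says.** **Masking.** Section 3.1 states: "The proposed study is a Randomized, single-masked, split-mouth, single center study". Section 5.7 says who is masked: "This is a single (subject) masked study". It adds one assessor: "Laboratory technicians will be masked when analyzing the bone core samples". Section 4.3 supports this with a code: "Bone specimens will be coded and not identifiable by laboratory personnel or clinical investigators in this study".

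**CBCT endpoint.** Section 3.3 makes volume stability the secondary endpoint: "We will be checking for bone volume stability through CBCT analysis comparing it from the time of placement, 8 months post-grafting", with a further comparison one year after implant insertion. Section 7.2 gives the measurement: "Radiographic examinations will be quantified by measuring bone height at three sites at each sinus augmentation site and then averaged for analysis". I take this to mean the CBCT scans, since section 3.3 names CBCT. Neither section names the person measuring, codes the images or mentions masking.

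**Who does what.** The opening of section 6 says: "All procedures will be performed by the study investigators who are licensed and privileged to do so". Section 6.2 has the randomization table used at the surgical visit to allot the grafts to sides, so whoever places them learns the allocation. Section 8.4 provides for the principal investigator to be unblinded if a serious adverse event occurs.

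**The concern.** The plan guards against observer bias for the cores but does not carry the safeguard over to the scans. Section 1.1 gives the rationale for adding small particles: more new bone without loss of graft volume. Core histology speaks to the first half of that claim. The CBCT comparison is the main quantified evidence on the second half; the secondary objective in section 2 also mentions clinical bone gain, but no method for it is given.

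Measuring graft height involves placing the measuring sites and judging where the graft ends. In a split-mouth trial both sides of the contrast may be visible in one image. A measurer who knows the allocation, and expects one graft to shrink more, could read the two sides differently without intending to.

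**Working it through.** **1. What is covered**

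| Assessment | Data coded? | Assessor masked? | Where |
|---|---|---|---|
| Core histology (primary) | Yes | Yes, technicians | 4.3, 5.7 |
| CBCT height/volume (secondary) | Not stated | Not stated | 3.3, 7.2 |
| Principal investigator | n/a | Implied until a serious adverse event (8.4); not among those masked in 5.7 | 5.7, 8.4 |

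**2. Which reading error causes bias**

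Let a height reading at time *t* equal the true height, plus an offset *c_t* that the measurer applies to both sides, plus a shift *d_t* applied only to the mixed-particle side because its allocation is known.

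- Paired difference at time *t*: true difference + (*c_t* + *d_t*) − *c_t* = true difference + *d_t*. The common offset cancels.
- Paired difference in change between times 1 and 2: true difference in change + (*d_2* − *d_1*). A shift that is the same at both times also cancels.

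So bias needs an allocation-linked shift and, for change over time, one that differs between the scans.

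**3. Illustration of size**

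The documents give no CBCT variance and no power figure for this endpoint. To check the method, I first reproduce the plan's histology figure (section 7.1): 10 pairs, two-sided paired t-test, alpha 0.05, 1 SD difference, 80% power. With 10 − 1 = 9 degrees of freedom and noncentrality √10 × 1 = 3.162, exact power is 80.3%, which agrees. This takes 1 SD as the SD of the paired differences, which equals the raw SD only if the within-subject correlation is 0.5.

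Now assume no true difference, the same test applied to the CBCT data, and a net allocation-linked shift of *b* SDs of the paired differences. The false-positive rate is the chance that a noncentral t with 9 degrees of freedom and noncentrality √10 × *b* falls outside the two-sided 5% limits.

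| Assumed *b* | √10 × *b* | False-positive rate |
|---|---|---|
| 0 | 0 | 5.0% |
| 0.10 | 0.316 | 5.9% |
| 0.25 | 0.791 | 10.9% |
| 0.50 | 1.581 | 29.3% |

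The values of *b* are assumptions. The table shows sensitivity at 10 pairs and does not estimate the bias in this trial.

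**4. Number of readings**

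10 subjects × 2 sinuses × 2 time points = 40 sinus readings. Of these, 20 come from the post-surgical research scans and 20 from the standard-of-care pre-implant scan. The one-year comparison in section 3.3 would add 20, making 60, but section 6 and Attachment A schedule no CBCT then, so I count two time points.

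**The case against.** The strongest case on the other side has five parts.

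- **No section says that an unmasked investigator measures the scans.** A reader might infer from the opening of section 6 that the operators will do so knowing the allocation. The documents do not support that: the sentence introduces the visit procedures and does not mention the measurement in section 7.2. Sections 3.1 and 6.1 place the scanning itself with the radiology department. This stands, and limits the point to what the plan permits.
- **Section 8.4 implies a masked principal investigator.** It does, but it covers one person, does not mention the scans, and disagrees with section 5.7. It is a reason to clarify, and does not settle the matter.
- **Measurement is already standardized.** Sections 3.1 and 6.1 use a radiographic guide for each patient, which limits discretion. That stands in part: section 7.2 does not tie the three sites to the guide, and a guide masks nobody.
- **A paired design removes reader error.** It removes error common to both sides, so the tempting claim that any systematic misreading passes into the comparison is wrong. An allocation-linked shift remains.
- **Coding may not mask fully.** Section 5.7 makes one graft half cortical and the other wholly cancellous, and section 1.4 calls cortical particles denser, so the scan may hint at the graft. A measurer who operated may also recall the sides. Both stand as limits on the remedy.

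**Conclusion.** The point holds as a gap in the plan. Masking is specified for subjects and for the technicians reading cores; it is unspecified for the CBCT measurements, and sections 5.7 and 8.4 disagree about the principal investigator. An unmasked comparison of the two sides would comply with the text as written.

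The consequence is confined to the secondary CBCT height/volume comparison. The primary histology has coded specimens and masked technicians, and the sample size is not touched. The direction and size of any bias cannot be derived from the documents. The conclusion rests on reading section 7.2 as describing the CBCT scans and on the absence of any other text that masks their measurement. This is a modest weakness that is cheap to remove, and it does not show that the volume results will be biased.

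**What to change.** In sections 5.7 and 7.2:

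- Extend the specimen-coding scheme to the CBCT files, so that they show no allocation, subject identity or time point.
- Fix the three height sites in advance from the existing radiographic guide or the implant plan.
- Have the sites measured in random order by someone without access to the randomization table or the code key. Section 4.3 keeps the specimen key where the study investigators can reach it, so say who holds the key for the scans.
- Name the measurer by role: where possible, a member of the existing team who did not operate on that subject.
- Reconcile section 5.7 with section 8.4 by stating whether the principal investigator is masked, and to what.

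The cost is minor file-coding work for about 40 sinus readings, with no new scan and no change in sample size. Because the grafts may be distinguishable on the image, the report should describe the reading as coded and say that masking may have been incomplete.

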Objectives.	The purpose of this study is to evaluate the influence of bone allograft particle size on bone vitality and bone volume in subjects undergoing sinus augmentation for the placement of dental implants.
Methodology	Randomized, split mouth
Study Duration	42 months
Participant Duration	24 months
Population	10 subjects, male or female, healthy
Study Sites	NYU College of Dentistry- clinic 5 W
Number of participants	10 participants expected to be enrolled

CONFIDENTIAL

This material is the property of the NYU College of Dentistry. Do not disclose or use except as authorized in writing by the study sponsor

Study Summary

Title	A RANDOMIZED, SPLIT MOUTH STUDY OF THE EFFECTS OF BONE GRAFT PARTICLE SIZE ON BONE VITALITY AND BONE VOLUME OUTCOMES IN SUBJECTS UNDERGOING SINUS AUGMENTATION FOR THE PLACEMENT OF DENTAL IMPLANTS
Short Title	Bone graft particle size on bone vitality and volume
Protocol Number	19-00996
Phase	Phase 2
Methodology	Randomized, single-masked, split-mouth, single center study
Study Duration	3.5 years
Study Center(s)	Single-center
Objectives	To determine the effects of small and large bone graft particles vs large particles alone on percent vital bone, percent residual graft material, measured histologically from bone biopsies of the grafted site taken at the time of dental implant placement from subjects undergoing sinus augmentation for the placement of dental implants. Dental radiographs taken post operatively will be used to estimate bone graft volume differences between conditions.
Number of Subjects	10
Diagnosis and Main Inclusion Criteria	Subjects have missing upper back teeth on both the left and right sides and insufficient bone height (<5mm) for dental implant placement
Study Product, Dose, Route, Regimen	Bone graft material will consist of four to six grams of commercially available human donor bone allograft (Puros Allograft Bone Particles, Zimmer Biomet, Warsaw, IN USA) consisting of cortical and cancellous bone chips of either 250-1000 microns, and 1000-2000 microns size, vs. 1000-2000 microns size alone.
Duration of administration	Bone graft material is implanted, dental implants are placed, restored and subjects are followed for a period of two years after implants are restored

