1.4 Treatment Planning

In this study, we will use cancellous and cortical allograft in a 50-50 ratio, and compare graft particle sizes. Due to their porous architecture, cancellous particles promote vessel penetration, allowing osteogenic cell movement and rapid re-vascularization. They also contain a lower density mineral component and higher collagen content, thus promoting quicker turnover. Since their high turnover rate can lead to significant volume loss, cortical particles, which are denser, are added to preserve the intended volume of the graft and to reduce shrinkage. The structural integrity of the cortical particles, the high mineral and low collagen contents, and their reduced turnover rate allow for space-maintenance, leading to decreased volume loss¹³. Using two different sizes of cancellous and cortical allograft will allow for comparison of histological and clinical outcomes, and help to define the optimal particle size graft material.

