1.5.1 Potential benefits

There will be no direct benefit to the subjects from the participation in the study. The knowledge gained from this study will help to define optimal grafting protocols, and therefore be a benefit to society.

2 Study Objectives

Primary Objective

To determine the effects of small and large bone graft particles vs large particles alone on percent vital bone, percent residual graft material, and bone graft volume, measured histologically from bone biopsies of the grafted site taken at the time of dental implant placement from subjects undergoing sinus augmentation for the placement of dental implants

Secondary Objective

To observe clinical and radiographic bone gain in order to calculate bone volume differences between conditions and the implant survivability.

3 Study Design

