5.1 Description

Bone graft material will consist of four to six grams of commercially available human donor bone allograft (Puros Allograft Bone Particles, Zimmer Biomet, Palm Beach Gardens, FL USA) consisting of cortical and cancellous bone chips of both 250-1000 microns, and 1000-2000 microns size, or 1000-2000 microns size alone. The method and composition of these products has been described, both products are FDA approved and commercially available. The harvesting and processing of the graft materials is briefly described as follows:

CONFIDENTIAL

This material is the property of the NYU College of Dentistry. Do not disclose or use except as authorized in writing by the study sponsor

Puros Allograft Bone Particles are sterile, dehydrated cortical and/or bone from donated human tissue. The donated human tissue utilized for this implant was recovered from a donor screened for risk factors associated with infectious diseases and medical conditions that rule out donation. The donor's blood was tested for relevant communicable diseases in a laboratory certified under the Clinical Laboratory Improvement Amendments of 1988 (CLIA) or equivalent and registered with the U.S. Food and Drug Administration (FDA) for donor testing. The following test criteria were met for this donor:

REQUIRED INFECTIOUS DISEASE TESTING BLOOD TEST ACCEPTABLE RESULT

- HIV-1 / HIV-2 Antibody Negative/ Non-Reactive
- Hepatitis C Virus Antibody Negative/ Non-Reactive
- Hepatitis B Surface Antigen Negative/ Non-Reactive
- Hepatitis B Core Antibody (Total) Negative/ Non-Reactive
- Syphilis Negative/ Non-Reactive
- Human T-Cell Lymphotropic Virus I/II Antibody Negative/ Non-Reactive
- HIV-1 NAT-TMA Negative/ Non-Reactive
- HCV NAT-TMA Negative/ Non-Reactive

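### The two grafts differ in bone type as well as particle size, so the trial as written cannot attribute a difference to particle size, which is its stated question

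*Combined protocol and SAP*

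**What the plan says.** **The question.** The Protocol Summary gives the purpose as to "evaluate the influence of bone allograft particle size on bone vitality and bone volume". The primary objective in Section 2 is "To determine the effects of small and large bone graft particles vs large particles alone on percent vital bone, percent residual graft material". Bone type appears in neither contrast. The title and the closing paragraph of Section 1.1 are also framed on particle size.

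**The grafts, as described in the background and device sections.** Section 1.4 states "we will use cancellous and cortical allograft in a 50-50 ratio, and compare graft particle sizes". Section 5.1, with near-identical text in Section 1.2, describes cortical and cancellous "bone chips of both 250-1000 microns, and 1000-2000 microns size, or 1000-2000 microns size alone". Read naturally, both arms contain both bone types and only size differs.

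**The grafts, as defined for randomization and surgery.** Sections 3.1, 5.7 and 6.2 agree with one another. One sinus receives equal quarters of small cortical, large cortical, small cancellous and large cancellous allograft. Section 5.7 defines the other as "Bone graft B: 100% large particle cancellous allograft for the contralateral sinus (N=10". Section 3.1 also says that the research element is "The use of different size and type (cortical or cancellous) of bone graft material for the two sites".

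**The analysis.** Sections 7.1 and 7.2 plan a two-sided paired t-test between the two conditions for percent vital bone and percent residual graft, at the 0.05 level, in 10 subjects.

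**The concern.** A split-mouth trial isolates particle size only if the two grafts are alike in everything else. Under Sections 3.1, 5.7 and 6.2, graft B also loses all of its cortical content.

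The protocol does not treat bone type as neutral. Section 1.4 describes cancellous particles as faster to revascularize and turn over, with a risk of significant volume loss, and says that "cortical particles, which are denser, are added to preserve the intended volume of the graft and to reduce shrinkage". Turnover and volume bear on residual graft, which is a primary outcome, and on CBCT volume stability, which is the secondary endpoint.

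Three readings of the result are at risk:

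- A significant difference could be reported as a particle-size effect when bone type produced it.
- A null result could be two opposing effects cancelling.
- Section 1.1 hopes that adding small particles raises new bone formation without loss of graft volume. Graft A also contains the cortical bone that Section 1.4 credits with preserving volume, so maintained volume in graft A would not show that small particles are volume-neutral.

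**Working it through.** **Step 1. Composition of each arm (Sections 3.1, 5.7 and 6.2).**

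| | Graft A | Graft B |
|---|---|---|
| Small cortical | 25% | 0% |
| Large cortical | 25% | 0% |
| Small cancellous | 25% | 0% |
| Large cancellous | 25% | 100% |
| **Small particles, total** | 25 + 25 = **50%** | **0%** |
| **Cortical, total** | 25 + 25 = **50%** | **0%** |

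**Step 2. What the paired difference estimates.** Let *s* be the small-particle share, *c* the cortical share, and *m* the subject's own level. Write a sinus's expected outcome as *m* + *s*·β_size + *c*·β_type + an interaction term in *s·c*. Graft A has *s* = *c* = 0.5 and graft B has *s* = *c* = 0. The expected A − B difference is

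0.5·β_size + 0.5·β_type + interaction.

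The variables *s* and *c* take identical values in all 20 sinuses (10 subjects × 2), so their correlation is 1 and only the sum can be estimated. Adding subjects adds more copies of the same contrast. No covariate helps, because there is no sinus in which one factor changes without the other. This applies to vital bone, residual graft and volume alike.

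**Step 3. The plan's own power figure.** Section 7.1 claims 80% power for a 1 SD difference in vital bone with 10 subjects. The exact noncentral-t calculation for a two-sided paired t-test uses n = 10, 9 degrees of freedom, α = 0.05 and noncentrality *d*·√n = 1 × √10 = 3.162. It gives 80.3%, which reproduces the stated figure. The match requires 1 SD to mean the SD of the paired difference. That equals the arm SD only if the within-subject correlation is 0.5, which the protocol does not state. By Step 2, this power belongs to the combined A-versus-B contrast, not to particle size.

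**Step 4. How far the result could mislead.** The documents give no size for the bone-type effect, so the values below are assumptions. Effects are in SDs of the paired difference, and the calculation is as in Step 3.

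| True size effect | Assumed bone-type effect | Net effect | Noncentrality | Chance of p < 0.05 |
|---|---|---|---|---|
| 0 | 0 | 0 | 0 | 5.0% |
| 0 | 0.25 | 0.25 | 0.791 | 10.9% |
| 0 | 0.5 | 0.5 | 1.581 | 29.3% |
| 0 | 0.75 | 0.75 | 2.372 | 56.2% |
| 0 | 1.0 | 1.0 | 3.162 | 80.3% |
| 1.0 | 0 | 1.0 | 3.162 | 80.3% |
| 1.0 | −0.5 | 0.5 | 1.581 | 29.3% |
| 1.0 | −1.0 | 0 | 0 | 5.0% |

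The fifth and sixth rows are identical: a pure bone-type effect of 1 SD and a pure size effect of 1 SD produce the same data. The last two rows show that a real size effect could be hidden by an opposing bone-type effect.

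**The case against.** There are four fair points on the other side.

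**It may be a drafting contradiction rather than a design.** If Sections 1.2, 1.4 and 5.1 state the intent, the composition of graft B is an error repeated in three places, and correcting it removes the confounding. That is possible. However, the randomization and surgical sections determine what is implanted, and they agree with each other.

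**The background text is ambiguous.** The 50-50 ratio in Section 1.4 matches graft A exactly and might describe only that mixture. Section 5.1 does not say outright which bone types the large-only graft contains. This stands, and it is why the sponsor must say which composition is intended. It does not alter the arithmetic for the arms as defined in Section 5.7.

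**The difference in type is disclosed, and A versus B is a valid comparison.** Section 3.1 says the sites differ in size and type, so the two-factor contrast may be deliberate. The paired test remains a sound randomized comparison of two compositions. This also stands. It moves the fault from the arms to the title, purpose and primary objective, which claim more than the contrast can deliver.

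**The bias may be small.** Section 1.4 is qualitative, gives no effect size, and does not directly say that bone type changes percent vital bone. The direction and size of any distortion are therefore unknown. That limits what can be said about magnitude but does not make the particle-size effect estimable.

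**Conclusion.** The concern holds. With the arms defined as in Sections 3.1, 5.7 and 6.2, small-particle share and cortical share are both 50% in graft A and 0% in graft B. The particle-size effect is therefore not identifiable for any outcome at any sample size. The stated 80% power applies to the combined contrast.

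The non-identifiability rests only on the compositions written in the protocol. The percentages for misleading results rest on assumed bone-type effects and on 10 complete pairs, and they are illustrations rather than forecasts. The within-subject comparison of the two compositions is unaffected. What fails is attribution to particle size, which is the primary question, so this needs correcting before the results are interpreted.

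**What to change.** First, reconcile the text so that one composition per arm appears everywhere. The sections to align are the title and short title, the Protocol Summary and Study Summary, Sections 1.1, 1.2, 1.4, 1.5, 2, 4.3 and 5.1 on one side, and Sections 3.1, 5.7 and 6.2 on the other. Which composition is intended is for the sponsor and investigator to state. Then take one of two routes:

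1. **If the cortical-to-cancellous content is meant to be the same in both arms,** correct the arm definitions in Sections 3.1, 5.7 and 6.2 so that only particle size differs. The existing title, objectives and analysis can then stand.
2. **If the compositions in Section 5.7 are intended,** restate the title, purpose, objectives and any conclusion as a comparison of two graft compositions (mixed-size cortical and cancellous versus large cancellous). Drop inference about particle size alone. The paired analysis needs no change.

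**Cost.** Route 2 is a text amendment with no added subjects or procedures, at the price of a narrower claim. Route 1 also adds no subjects or procedures if no one has yet been grafted. It does change what is implanted in one sinus, so the amendment needs IRB review under Section 11 and the consent text should be checked. The protocol does not give enrolment status. For subjects already treated under Section 5.7, only the narrower claim is available, and changing the arms midway would mix compositions within a sample of 10.
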